7.1.3. Physical Examinations

Physical examinations are to be performed at the Baseline visit (last visit in Study A1281198) and at Week 26 (or early termination). Any significant physical examination finding should be recorded as an adverse event.

7.1.4. Blood Pressure and Pulse

Blood pressure will be measured in the dominant arm (as defined by the subject, parent or legal guardian) and recorded to the nearest whole numbers. Pulse rate will be measured for at least 30 seconds. Two measurements will be obtained at each visit: once while the subject is in a sitting position and then in a standing position to assess orthostatic effects. The subject should be in the sitting position for approximately 5 minutes and in the standing position for approximately 2 minutes before the measurements are obtained.

7.1.5. Body Weight and Height, BMI, Waist Circumference

Body weight, height, and waist circumference will be measured at the Baseline visit and at Week 6 and 26 (or early termination). All measurements should be taken with the subject wearing only light indoor clothing and without shoes. Height will be measured with a stadiometer; weight will be measured with a standard physician's scale. Investigators will calculate the subject's Body Mass Index (BMI) from height and weight. A BMI and BMI z-score calculator will be provided within the Firecrest site.

BMI z-score will be used to evaluate changes in body weight. An increase in the BMI z-score (adjusted for age) of 1 or more is to be documented as an adverse event in the subject's eCRF. All BMI calculations are to be recorded by the investigator in the source documents and eCRF.

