Safety data from this trial will be monitored by the independent Data Monitoring Committee (DMC) currently monitoring study A1281198. Details of the board's functions are documented in the DMC Charter.

SCHEDULE OF ACTIVITIES

The schedule of activities table provides an overview of the protocol visits and procedures. Refer to the **STUDY PROCEDURES** and **ASSESSMENTS** sections of the protocol for detailed information on each procedure and assessment required for compliance with the protocol.

The investigator may schedule visits (unplanned visits) in addition to those listed on the schedule of activities table, in order to conduct evaluations or assessments required to protect the well-being of the subject.

Activities/ Assessments	Baseline ^a	Open-label Ziprasidone										Follow up Visit	Follow Up ¹
		± 1 Day					±3 days						
Visit	1	2	3	4	5	6	7	8	9	10	11	12	
Visit Schedule	Day 1	W1	W2	W4	W6	W10	W14	W18	W22	W26/ ET ^a		W27	
Informed Consent, Assent ^c	X												
Inclusion/Exclusion	X												
Physical Exam	X										X		
Body Weight/Height/ BMI/BMI-z score/ waist circumference	X				X						X	X ^d	
ECG ^{*e}	X	X	X	X	X		X		X	X	X	X ^d	
Blood Pressure/Pulse ^f	X	X	X	X	X	X	X	X	X	X	X	X ^d	
Chem/Hemato/Urinalysis	X				X						X	X ^d	
Hormones (free T4 & TSH, Prolactin)	X				X						X	X ^d	
Fasting glucose, lipids, insulin, HbA1c ^{**}	X				X			X			X	X ^d	
Urine drug screen ^g	X				X						X		
Urine Pregnancy Test ^h	X	X	X	X	X	X	X	X	X	X	X	X	
Verification of contraception	X	X	X	X	X	X	X	X	X	X	X	X ⁱ	
Dispense Double-Blind Transition Card ^{j,m}	X	X ^{m,j}											
Dispense Study Drug	X	X	X	X	X	X	X	X	X				
Drug Accountability		X	X	X	X	X	X	X	X	X			
Subject telephone contact ⁱ		X	X			X	X	X	X	X		X ⁱ	
YMRS	X	X	X		X		X		X	X			
CGI-S	X	X	X	X	X	X	X	X	X	X			
CGAS	X										X		
CDRS-R	X	X	X	X	X	X	X	X	X	X	X ^d		
SARS, BAS, AIMS	X	X	X	X	X	X	X	X	X	X	X ^d		
C-SSRS ^k	X	X	X	X	X	X	X	X	X	X	X		
Serious and non-serious adverse event monitoring	X	X	X	X	X	X	X	X	X	X	X	X ⁱ	
Concomitant Medication	X	X	X	X	X	X	X	X	X	X	X	X	

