2. STUDY OBJECTIVES AND ENDPOINTS

Primary Objective(s):	Primary Endpoint(s):

 To assess the safety and tolerability of oral ziprasidone (20-80 mg BID) during long term, open label administration in children and adolescents with Bipolar I Disorder who participated in Study A1281198. 	
 Safety Assessments; Adverse event reporting; Clinical laboratory testing; Physical examinations; Blood pressure and pulse; Height and weight; Body Mass Index (BMI) and BMI Z score; Waist circumference; Electrocardiograms, including QTc; Special Safety Assessments; Movement Disorder Scales (SARS, BAS, and AIMS); Columbia Suicide Severity Rating Scale (C-SSRS); Child Depression Rating Scale (CDRS-R); Efficacy Assessments; Young Mania Rating Scale; Clinical Global Impression of Severity (CGI-S); Children's Global Assessment Scale (CGAS).

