5.6. Summary of the Dose Titration Schedule for Study A1281201

1. No dose adjustments are allowed during Week 1 of the Dose Transition period (for either the <45 kg or ≥ 45 kg dose category); subjects who cannot tolerate the Week 1 dose titration should be withdrawn from the study.
2. Weekly dose adjustments (increases or decreases) are allowed from Week 2 of the Dose Transition period to the end of the study (Week 26). In general, dose adjustments should not occur more frequently than every 7 days to provide an adequate period of time to evaluate the clinical effect of the dose adjustment. Dose adjustments are achieved by issuing an open label fixed dosing card to the subject (ie, with a total daily dose of 40 mg, 60 mg, 80 mg, 100 mg, 120, 140 mg, or 160 mg).
3. The dose may be increased if the subject has been tolerating the current dose level without significant side effects; but, in the clinical judgment of the investigator, has had an insufficient clinical efficacy response. The clinical rationale for the dose increase should be documented in the source documentation for the subject.

4. In general, dose increases should not exceed 20 mg. However, subjects weighing ≥ 45 kg may be increased to 140 mg or 160 mg total daily dose if they have tolerated the 120 mg dose well, have reached Day 15 of the study, and have had an insufficient clinical efficacy response to the 120 mg total daily dose.
5. The dose may be decreased if, in the clinical judgment of the investigator, the subject is not tolerating the current dose well and is likely to benefit from continued treatment with a lower dose of study drug that may be better tolerated. There is no limit on the number of dose decreases; however, subjects who cannot tolerate a minimum total daily dose of 40 mg should be withdrawn from the study. The clinical rationale for the dose decrease should be documented in the source documentation for the subject. In general, dose decreases should not exceed 40 mg.
6. Subjects who, in the clinical judgment of the investigator, have reached their maximum tolerated dose and still have an insufficient clinical response should be withdrawn from the study.

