6.2. Study Visits During Open-label Treatment

Subjects will attend study visits at Weeks 1, 2, 4, 6, 10, 14, 18, 22, and 26 (or early termination). There will also be a brief follow-up (off treatment) visit at Week 27. The following will be assessed or administered at EVERY on-treatment visit:

- Adverse events;
- Review of concomitant medications;
- Blood pressure and pulse;
- Drug accountability (Document drug returned and record any dosage changes, except Day 1);
- Dispense study drug (except Week 26 or early termination);
- Double-blind transition card provided only for ≥ 45 kg weight group subjects (Week 1);
- CGI-S;
- C-SSRS;

- CDRS-R;
- Movement disorder scales (SARS, BAS, AIMS);
- A urine pregnancy test will be obtained on all female subjects at all study visits. A positive urine pregnancy test should be confirmed with a serum pregnancy test.
- Verification of contraception.

At week 4 in addition to the above the following will be assessed or administered:

- Electrocardiogram.

At Weeks 1, 2, 6, 14, 22 and 26 (or early termination), in addition to the above, the following will be assessed or administered:

- YMRS;
- Electrocardiogram.

At Weeks 6 and 26 (or early termination), in addition to the above, the following will be assessed or administered:

- Clinical laboratory tests (chemistry, hematology, urinalysis) and urine drug screen;
- Body weight, height, BMI, BMI z score, and waist circumference;
- Hormones (free T4 & TSH (thyroid stimulating hormone), Prolactin).

At Weeks 6, 18, and 26 (or early termination), in addition to the above, the following will be assessed or administered:

- Fasting glucose, lipid profile, insulin and glycated hemoglobin (HbA1c).

The following will be done only at Week 26 (or early termination):

- Physical exam;
- CGAS.

A urine pregnancy test will be obtained on all female subjects at all study visits. A positive urine pregnancy test should be confirmed with a serum pregnancy test.

Following the baseline visit, unscheduled urine drug screens can be performed at additional visits at the investigator's discretion.

Since no investigational product will be available after the Week 26 visit, the physician may initiate appropriate treatment with commercially available medications.

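### Weight and height could be added cheaply at Weeks 10, 14, 18 and 22: for a completer, the BMI z-score adverse-event rule can be applied by schedule only at Weeks 6 and 26

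*Protocol*

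**What the plan says.** Three places in the protocol give the same schedule for weight, height, BMI, BMI z-score and waist.

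- Section 7.1.5: "Body weight, height, and waist circumference will be measured at the Baseline visit and at Week 6 and 26 (or early termination").
- Section 6.2 lists these measures under "At Weeks 6 and 26 (or early termination), in addition to the above".
- The Schedule of Activities row "Body Weight/Height/ BMI/BMI-z score/ waist circumference" fits this. It adds a Week 27 repeat only for a subject with an earlier abnormal finding that needs follow-up.

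Other provisions bear on the point:

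- Section 2 puts "Body Mass Index (BMI) and BMI Z score" in the primary endpoint column, with height, weight and waist.
- Section 7.1.5 explains the use of the measure ("BMI z-score will be used to evaluate changes in body weight") and sets the rule: "An increase in the BMI z-score (adjusted for age) of 1 or more is to be documented as an adverse event".
- Section 5.6, item 2, on dose: "Weekly dose adjustments (increases or decreases) are allowed from Week 2 of the Dose Transition period to the end of the study (Week 26").
- Section 6.2 schedules the fasting metabolic panel separately: "At Weeks 6, 18, and 26 (or early termination), in addition to the above". Week 18 therefore has a panel but no weight.
- SAP 6.5.4 summarises these data by time point, with frequency tables for a one-point rise in BMI z-score. It adds no measurement occasion.

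**The concern.** The study exists to obtain longer-term pediatric safety data. Protocol 1.2 names weight gain among the drawbacks of several antipsychotics already approved for pediatric mania. For ziprasidone itself, section 1.2.1 offers a receptor-affinity argument and adult data. Weight in children is thus something the study should describe well.

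Yet the protocol's own z-score rule cannot be applied on schedule between Week 6 and Week 26, although the child attends four clinic visits in that time. Section 8.1.5 requires a causality judgement for every adverse event. If a z-score event first appears at Week 26, the investigator cannot say which dose the child was taking when it began. A rise that came and went would leave no scheduled record.

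**Working it through.** **Inputs.** Measurement weeks 0, 6 and 26 (protocol 6.2 and 7.1.5). Clinic visits at Weeks 1, 2, 4, 6, 10, 14, 18, 22 and 26 (6.2). About 55 entrants, about 35% dropout and about 40 completers (9.1).

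**The plan's completer figure.** 55 × (1 − 0.35) = 35.75, about 36. This does not reproduce the stated 40, since 40/55 implies 1 − 0.727 = 27% dropout. The point does not rest on this figure, so the range of 36 to 40 completers is carried forward. The other 15 (55 − 40) to 19 (55 − 36) are measured at ET if they attend.

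**Gaps for a completer.**

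| Measurement weeks | Intervals (weeks) | Longest after Week 6 | On-treatment measurements |
|---|---|---|---|
| 0, 6, 26 (current) | 6, 20 | 20 | 2 |
| 0, 6, 18, 26 | 6, 12, 8 | 12 | 3 |
| 0, 6, 10, 14, 18, 22, 26 | 6, 4, 4, 4, 4, 4 | 4 | 6 |

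The current gap is 20/26 = 77% of treatment, or 20 × 7 = 140 days (134 to 146 if a ±3-day window applies at both ends). The clinic visits inside it are Weeks 10, 14, 18 and 22.

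**Dose changes inside the gap.** At one change per 7 days the ceiling is 140/7 = 20. The realistic number is not given and is probably far lower.

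**Does anything else fill the gap?**

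- Unplanned visits are allowed, but at the investigator's discretion, and no weight is specified for them.
- The Week 27 repeat is conditional, off treatment and after the gap.
- Adverse events are asked about at each visit, and telephone contacts fall at about Weeks 8, 12, 16, 20 and 24. Neither yields a z-score.
- ET visits shorten the gap for early leavers who attend. Section 6.4 requires the visit to be scheduled, but it also provides for subjects lost to follow-up.

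**The case against.** The strongest reply is that this is a preference about visit frequency. The sections agree, no planned table fails, and a persistent rise is still recorded at Week 26 or ET. Finding it sooner triggers no required action beyond recording it. All of that stands.

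Primary-endpoint status also carries little weight alone, because that column lists every safety and efficacy assessment. Routine chemistry, hematology, urinalysis, thyroid hormones and prolactin share the gap, and physical examination and CGAS have nothing scheduled between Baseline and Week 26/ET. This is fair, but it does not defeat the point: a weight needs no blood draw, and 7.1.5 ties a numerical adverse-event rule to it.

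A reader might infer more than the documents support:

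- **That onset and dose relation are lost.** Onset is bracketed between Weeks 6 and 26. Section 5.5 insists that the date of each dose change be recorded, so the dose history is known. Noticeable weight gain can also be reported at any visit with its own onset date. What is missing is the position of a z-score event within the window.
- **That 20 dose changes will occur.** Twenty is a ceiling. Cards are dispensed every four weeks from Week 6, a change means issuing a different card, and increases need a documented clinical reason. Section 5.5 recommends an unscheduled visit when a change is needed, though it does not ask for a weight there.
- **That a planned dose or onset analysis is undermined.** The SAP plans none.
- **That transient rises are common.** Nothing in the documents shows how often a full z-score unit would be gained and then lost within 20 weeks.

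**Conclusion.** The point holds as a cheap improvement to a design choice, not as a correction of an error. For about 36 to 40 completers, the z-score rule operates by schedule at two on-treatment visits 20 weeks apart. The consequence is imprecise dating of persistent rises after Week 6, and possible non-recording of rises that reverse or that occur in subjects who leave without an ET visit. The size of that second effect cannot be derived from the documents.

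The conclusion assumes that sites follow the schedule and do not routinely weigh at other visits. The 20-week interval does not depend on the dropout assumption; only the number of children with the full gap does.

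**What to change.** In the Schedule of Activities, 6.2 and 7.1.5, add body weight and height at the existing Week 10, 14, 18 and 22 visits, with BMI and BMI z-score derived from them. In 7.1.5 the occasions would then read: weight and height at Baseline and Weeks 6, 10, 14, 18, 22 and 26 or ET. Waist at Week 18 is optional.

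Adding Week 18 alone would give each fasting panel a same-visit weight, but it is only a partial remedy. It leaves gaps of 12 and 8 weeks, so the dose at onset could still be uncertain, and no planned analysis links the panel to weight.

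The cost is a few minutes per visit with the scale and stadiometer already in use: at most 4 × 55 = 220 extra measurement occasions, or 4 × 36 = 144 to 4 × 40 = 160 among completers. Extra CRF fields and a protocol amendment with IRB/EC approval are also needed. No new visit or sample is required, and SAP 6.5.4 can take the added time points without a change of method.

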7.2. Electrocardiograms

A 12-lead ECG will be obtained from each subject at Weeks 1, 2, 4, 6, 14, 22 and Week 26 and repeated at the follow-up visit if abnormalities were present at the Week 26 (or early termination) visit. Baseline ECG data will be obtained from A1281198 final study visit.

The subject must fast at least 3 hours before ECGs are obtained. ECGs must be obtained prior to the collection of any blood sample because drawing blood can affect the ECG. To standardize the collection procedure, the ECG should be collected in a comfortable and quiet place after the subject has been allowed to rest in a supine position for approximately 5 minutes.

All ECGs must be reviewed for safety at the site by a physician qualified to read and interpret the results (ie, a pediatric cardiologist, or an adult cardiologist experienced in the interpretation of pediatric ECGs should be contacted to discuss the ECG). This assessment will include the calculation of QTcF. ECGs must be reviewed on the day of the recording, signed and dated by the reader, and retained in the subject's study records.

ECGs in this study will be collected with an ECG recorder to be supplied to the site. This machine can generate a hard copy tracing, as well as digitally transmit via a modem to a central ECG service (BMS- BioMedical Systems). Standardized site and subject identification information have to be entered into the machine by the ECG technician prior to each recording. The electronic version transmitted to BMS will be the same as the hard copy. BMS will provide clinical interpretation and overread designated parameters (Heart Rate (HR), PR, Respiration Rate (RR), QRS QT, QTcF, QTcB).

ECGs showing a QTcF of ≥ 480 msec or a suspected increase from baseline of 60 msec or greater must be repeated within the same visit. If the QTcF value persists at ≥ 480 msec and/or the change from baseline persists at ≥ 60 msec, the study drug must be discontinued immediately and a pediatric cardiologist or an adult cardiologist experienced in the interpretation of pediatric ECGs should be contacted to discuss the ECG result.

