The blister cards for Weeks 3-26 will each contain medication for 8 days. Two blister cards will be dispensed at Weeks 2 and 4 and then 4 blister cards will be dispensed at each monthly visit from the Weeks 6 visit through the Week 22 visit. Dose increases should be limited to 20 mg a week during Weeks 6-22 of the flexible dosing weeks of the study. However, subjects ≥ 45 weight can be increased to 160 mg a day after they have been on a stable dose of 120 mg a day if clinically indicated. [Table 1](#), [Table 2](#), [Table 3](#) and [Table 4](#) provide the dose transition schedule for all possible dose levels for subjects in both weight categories.

Statistical Methods:

Sample Size

The number of subjects entering this open-label trial will be determined by the number of subjects electing to continue treatment after completing or withdrawing from the preceding double blind study, A1281198. We estimate that approximately 55 subjects randomized in the double blind study (based on the increased sample size of N (number) =194 subjects) will be eligible to continue in this open label extension. With an expected dropout rate of approximately 35%, this gives an estimate of approximately 40 subjects to complete this 26 week open label study (if all 55 subjects enter the extension study).

Data Summarization Methods

As this is an open label study with no comparator, no inferential statistics will be performed. Quantitative variables will be described by standard descriptive statistics (n, mean, standard deviation, minimum, and maximum, 95% confidence intervals), and qualitative variables will be summarized by frequency tables. Summaries will include data for all subjects who took at least one dose of investigational product in this open label extension study.

Baseline values for efficacy, outcomes and special safety endpoints will be the last observation made prior to the subject's receiving open label treatment. For safety, for those subjects who were randomized to placebo in the double blind study, baseline values will be

the last observation prior to initiating dosing in the open label extension study (normally, the observation of the last visit in the double blind study); and for those subjects who were randomized to ziprasidone in the double blind study, baseline values will be the last observation prior to initiating dosing in the double blind study (normally, the value from the Baseline visit in the double blind study).

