ET = early termination; BMI = Body Mass Index; ECG = Electrocardiogram; T4 = Thyroxin 4; TSH= Thyroid-Stimulating Hormone; HbA1c = glycated hemoglobin; YMRS = Young Mania Rating Scale; CGI-S = Clinical Global Impressions of Severity; CGAS =Children's Global Assessment Scale; CDRS-R = Child Depression Rating Scale - Revised; SARS = Simpson Angus Rating Scale; BAS = Barnes Akathisia Rating Scale; AIMS = Abnormal Involuntary Movement Scale; C-SSRS = Columbia Suicide Severity Rating Scale.

* All ECGs will be administered at least 3 hours after food intake.

** Subjects should remain fasting for at least 8 hours prior to the baseline visit, Week 6, Week 18, and Week 26..

- a. Baseline Visit is the last visit of the preceding double-blind trial, Study A1281198. In the case of early termination, all procedures specified for Week 26/ET are to be completed.
- b. Every effort should be made to bring the subject back to the office on the designated study days; however, monthly office visits will have a ± 3 day visit window to allow for slight variations in subject schedules. When scheduling subsequent visits, the overall treatment period in the protocol should be maintained.
- c. Subjects who turn 18 years old during the study need to give a written consent.
- d. Only if the subject had clinically significant abnormal findings from a previous visit that require follow-up.
- e. ECGs showing a QTcF of >480 msec or a suspected increase from baseline of 60 msec or greater must be repeated within the same visit. If the QTcF value persists at >480 msec and/or the change from baseline persists at >60 msec, the study drug must be discontinued immediately and a pediatric cardiologist or an adult cardiologist experienced in the interpretation of pediatric ECGs should be contacted to discuss the ECG result.
- f. The subject should be in the sitting position for approximately 5 minutes and in the standing position for approximately 2 minutes before the measurements are obtained.
- g. Following the baseline visit, unscheduled urine drug screens can be performed at additional visits at the investigator's discretion.

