3. STUDY DESIGN

This 26 week open label extension study is designed to provide information on the safety and tolerability of oral ziprasidone (20 to 80 mg BID with meals) during long term administration in children and adolescents with Bipolar I Disorder (current or most recent episode manic). It will enroll subjects who have participated in the 4 week, double blind, placebo controlled safety and efficacy trial, Study A1281198, meet study entry criteria, and wish to receive treatment with open label ziprasidone.

The number of subjects entering this open-label trial will be determined by the number of subjects electing to continue treatment after completing or withdrawing from the preceding double blind Study A1281198. We estimate that approximately 55 subjects randomized in the double blind study (based on the increased sample size of N=194 subjects) will be eligible to continue in this open label extension. With an expected dropout rate of approximately 35%, this gives an estimate of approximately 40 subjects to complete this 26 week open label study (if all 55 subjects enter the extension study).

The final visit of the double blind trial (Week 4 or early termination visit from A1281198) will serve as the Baseline Visit for the extension study. The first 1-14 days of Study A1281201 will be considered a transition period during which the study drug will continue to be administered under double-blind conditions. During this double-blind transition period, subjects who were on placebo in Study A1281198 will be provided active medication that will allow them to be titrated up to the appropriate weight-adjusted target dose, following titration schedule that was employed in Study A1281198. Subjects who were on active medication (ziprasidone) at the end of Study A1281198 will continue on that treatment course under double-blind conditions. At the end of the double-blind transition period, all subjects will receive open label ziprasidone.

Any subject who cannot tolerate the transition study medication during Week 1 should be discontinued from the study.

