5.1. Allocation to Treatment

Throughout most of this study, ziprasidone will be administered as open label (OL) investigational product to all subjects.

However, the dose transition from the double-blind study drug administered in Study A1281198 to the open-label dosing in the extension trial A1281201 will be conducted under double-blind conditions.

The double-blind dose transition phase of Study A1281201 will comprise Weeks 1 and 2 for subjects ≥ 45 kg and Week 1 for subjects < 45 kg. The double-blind (DB) medication for this transition period will be assigned according to the subject's randomization number in the preceding study so that the investigator remains blinded during this period.

At the baseline visit of the A1281201 study, subjects will transition onto active medication if previously assigned to the placebo group or continue on active study drug. Over the course of the double-blind dose transition period, subjects < 45 kg will be transitioned to a total daily dose of 60 mg a day by Day 7 of Week 1 and subjects ≥ 45 kg will be transitioned to a total daily dose of 120 mg a day by Day 10 of Week 2. (Subjects on 160 mg, 140 mg, 100 mg, and 80 mg active at the end of Study A1281198 will all be transitioned to 120 mg a day at the

end of the two-week transition period. Subjects on 120 mg active at the end of Study A1281198 will remain on 120 mg a day through the dose transition period).

Any subject who cannot tolerate the transition study medication during Week 1 should be discontinued from the study.

All medication will remain blinded until the end of the transition period. Diagrams of the transition dosing cards for subjects who were on placebo or ziprasidone in Study A1281198 are provided in [Table 1](#), [Table 2](#), [Table 3](#) and [Table 4](#).

At the end of the double-blind transition period, all subjects will start to receive open label ziprasidone. Diagrams of the double-blind dose transition study drug blister cards are provided in [Table 1](#), [Table 2](#), [Table 3](#) and [Table 4](#).

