Syncope	All syncopal episodes suggestive of cardiac arrhythmia (sudden loss of consciousness, loss of postural tone, and no pre-syncopal phase), except vasovagal syncope will be considered adverse events and the subject will be discontinued from the study. Every effort should be made to obtain vital signs and an electrocardiogram at the time of the event. Further evaluation, eg, Holter monitoring, may also be useful. Subjects experiencing syncope of probable vasovagal origin (onset not sudden but preceded by a pre-syncopal phase, presence of predisposing factors such as blood sampling procedure, standing, hot shower, hair curling, etc) will also be considered adverse events but subjects may continue study participation after sponsor approval.

Event	Criteria
Prolonged QT	
Electrocardiograms are to be reviewed and compared to baseline to assess potential changes. ECGs showing a QTcF of ≥ 480 msec or a suspected increase from baseline of 60 msec or greater must be repeated within the same visit. If the QTcF value persists at ≥ 480 msec and/or the change from baseline persists at ≥ 60 msec, the study drug must be discontinued immediately and a pediatric cardiologist or an adult cardiologist experienced in the interpretation of pediatric ECGs should be contacted to discuss the ECG result.
 
A verified increase in QTcF of ≥ 60 msec or a verified occurrence of QTcF ≥ 480 msec will be considered as an adverse event of QTc prolongation. QTcB (Bazett's correction) prolongation will not be used to define adverse events; QTcB will be measured only to enable historical comparisons.

Ventricular arrhythmia	
An ECG showing ventricular arrhythmia (except single ventricular extrasystoles) should be followed up with a rhythm strip ECG and Pfizer must be notified. In addition, a stat over read from the central vendor should be requested, a pediatric cardiologist or adult cardiologist experienced in the diagnosis and treatment of pediatric arrhythmias should be consulted, and the subject monitored, as necessary. If the ventricular arrhythmia is confirmed, the subject must be discontinued from the study.

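### The reference ECG for the 60 msec QTcF stopping rule is inconsistent; on the more natural site reading, a cumulative rise of 60 msec or more can meet neither mandatory limit

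*Protocol*

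**What the plan says.** **What sites are told.** Protocol 7.2 states "Baseline ECG data will be obtained from A1281198 final study visit". Footnote a of the Schedule of Activities agrees: "Baseline Visit is the last visit of the preceding double-blind trial, Study A1281198".

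**The stopping rule.** It appears in footnote e, in the Prolonged QT row of 6.4 and in 7.2. In all three, "a suspected increase from baseline of 60 msec or greater must be repeated within the same visit". If the finding persists on repeat, drug stops. Sections 6.4 and 7.2 set the limits at ≥480 msec and ≥60 msec; footnote e has "persists at >480 msec and/or the change from baseline persists at >60 msec". The adverse-event sentence in 6.4 ("A verified increase in QTcF of ≥ 60 msec or a verified occurrence") names no reference visit. None of the three places says which ECG is the baseline for the change.

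**Drug status at the final visit.** Section 3: "Subjects who were on active medication (ziprasidone) at the end of Study A1281198 will continue on that treatment course under double-blind conditions". The final-visit ECG is therefore on drug for these subjects.

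**What the analysis uses.** For ziprasidone-randomized subjects, the Protocol Summary and section 9 say "baseline values will be the last observation prior to initiating dosing in the double blind study". SAP 3.4 makes ECG an exception to its general baseline and assigns it the A1281198 Baseline visit for everyone. SAP 6.5.6 then tabulates QTcF rises of ≥30, ≥60 and ≥75 msec from that value.

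**Entry.** Exclusion 1 removes subjects with a confirmed, persistent parent-study QTcF above 480 msec or a rise above 60 msec.

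**The concern.** The analysis measures drug effect from a pre-drug ECG, but the wording beside the stopping rule points sites to an ECG that may already carry part of that effect. A parent-study rise too small for Exclusion 1 can be carried into the extension, and the site's 60 msec count then restarts from the raised value.

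At stake is a child who stays on drug with a cumulative QTcF rise that the sponsor's own table would place in the ≥60 or even the ≥75 msec category, with no mandatory repeat ECG, QTc adverse event or discontinuation. Dose can also rise after the final visit: subjects of at least 45 kg on 80 or 100 mg move to 120 mg during the transition (section 5.1), and 160 mg is later allowed (section 5.6). Long-term safety is the primary objective and QTc is a named endpoint.

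**Working it through.** The plan gives no figure to reproduce here. The check is threshold algebra in whole msec.

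**Inputs**
- B = pre-drug QTcF (A1281198 Baseline); F = QTcF at the A1281198 final visit; E = QTcF in the extension.
- r = F − B. Exclusion 1 limits a confirmed carried-in rise to r ≤ 60, taking its baseline to be the parent-study Baseline.
- Site limits (6.4, 7.2), with the final visit as reference: E ≥ 480 or E − F ≥ 60.
- Analysis event (SAP 3.4 and 6.5.6): E − B ≥ 60.

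**Range that meets neither site limit**

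An analysis event goes untriggered when B + 60 ≤ E < min(480, B + r + 60).

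Subtracting B, the cumulative rise runs from 60 up to just under min(480 − B, 60 + r). This range is non-empty only if r > 0 and 480 − B > 60, that is, B < 420. A 1-msec grid gave the same boundary: the largest B with an untriggered event was 419 and the smallest r was 1.

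**At B = 395** (480 − 395 = 85)

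| r | min(85, 60 + r) | Untriggered cumulative rise |
|---|---|---|
| 0 | 60 | none |
| 10 | 70 | 60–69 |
| 20 | 80 | 60–79 |
| 35 | 85 | 60–84 |

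**Worked case, B = 395 and F = 430** (r = 35, so Exclusion 1 is passed)
- Untriggered values of E run from 395 + 60 = 455 to 479.
- E = 460: site 460 − 430 = +30; analysis 460 − 395 = +65.
- E = 472: site 472 − 430 = +42; analysis 472 − 395 = +77, the ≥75 category.

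**When a rise of ≥75 can be missed.** It needs 60 + r > 75, so r ≥ 16, and B + 75 ≤ 479, so B ≤ 404.

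**Upper bound.** With r ≤ 60 the untriggered rise is always below 60 + 60 = 120 msec. The 480 limit tightens this as B rises: with r = 40 the largest untriggered rise is 99 at B = 380, 79 at B = 400 and 69 at B = 410. At B = 420 it is 59, so no analysis event is missed.

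**If the site reference were B.** Every E − B ≥ 60 would meet the site limit, so the range is empty for all B and r.

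**Check of the remedy.** A rule met by ≥60 from either B or F contains the current final-visit rule, so it loses no trigger, and it catches every E − B ≥ 60. A rule on B alone would lose triggers: B = 410, F = 395, E = 457 is +62 from F but only +47 from B. One side effect appears at the entry limit. B = 400 and F = 460 is exactly +60, so it passes Exclusion 1 as worded (above 60), yet an unchanged, confirmed 460 at Week 1 would already meet the either-reference stop.

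**The case against.** The strongest reply is that the gap exists on one reading only. The Protocol Summary and section 9 give the protocol's only explicit, arm-specific definition of a safety baseline, and section 9 mentions ECG by name in the placebo clause. If the rule's baseline carries that meaning, nothing is missed in ziprasidone-randomized subjects. The 7.2 sentence could also be read as saying only that no separate baseline ECG is taken.

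That reading is possible, so it would be wrong to infer that sites are definitely told to use the on-drug ECG. The final-visit reading is still the more natural one. Section 7.2 names the baseline ECG next to the rule, whereas section 9 defines baselines for data summaries. The section 9 definition also depends on parent-study arm, and the transition medication is assigned "so that the investigator remains blinded during this period", a period that includes ECG visits.

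Safeguards also exist:
- the absolute 480 msec limit;
- Inclusion 4;
- same-day physician review and central overread;
- the monitoring committee, which also oversees A1281198;
- optional sponsor reviews (9.4);
- investigator or sponsor discretion to record an abnormal test as an adverse event (8.2.2).

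These reduce the risk. None is stated to require comparison with the pre-drug ECG. The committee charter, the parent protocol and any central-ECG alert rules are not available here, so one cannot infer that no such comparison happens in practice.

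A reader might also infer a second gap at exactly 480 msec from footnote e's wording. The documents do not support that. The Schedule is described as an overview that defers to the detailed sections, and both 6.4 and 7.2 use ≥480. The mismatch is a drafting inconsistency to harmonize.

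**Conclusion.** The concern holds in a limited form: the reference for a mandatory QTcF stopping rule is inconsistent, and on the more natural site reading the rule can leave a cumulative rise of 60 msec or more without triggering. This should be fixed.

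The result rests on three assumptions: sites use the final-visit ECG, QTcF had already risen by that visit, and pre-drug QTcF was below 420 msec. A small carried-in rise opens only a narrow window: at r = 10, QTcF must rise a further 50 to 59 msec in the extension.

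The number of subjects affected cannot be derived, because the documents give no QTcF distribution. About 55 subjects are expected to enter, and only the ziprasidone-randomized part has an on-drug final-visit ECG. All the worked values are illustrations.

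A reader might infer that the reported QTc results are biased. They are not biased by this: SAP 3.4 and 6.5.6 count these rises from the pre-drug ECG whatever the site does. The issue is subject protection during treatment.

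**What to change.** In 6.4, 7.2 and footnote e, state that the change criterion is met by a confirmed QTcF rise of ≥60 msec from either the A1281198 Baseline (pre-drug) ECG or the A1281198 final-visit ECG, for every subject. Use ≥480 and ≥60 msec in all three places. Align Exclusion 1 to the same limits, so that no subject is eligible at entry while already at the stopping limit.

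Because one rule applies to all subjects, no unblinding is needed. Exclusion 1 already turns on the parent-study change and 6.1 makes the investigator confirm eligibility, so sites should already hold the pre-drug QTcF or the change from it.

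The cost is a wording change in four protocol places, some more same-visit repeat ECGs, possibly a few more discontinuations, and rare extra exclusions at exactly +60 or 480 msec. Subjects entering with a large carried-in rise will have little headroom: at +50, a further 10 msec meets the limit.
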